While evidence in the literature is scant, there is no clear consensus on the need and efficacy of heparinized saline as the solution for maintaining patency in implanted port catheters (Camp-Sorrell, 2010). The investigators in this study examined the community standard, which revealed that while some area hospitals do use heparin in the final flush solution for implanted port

catheters, others adopted a saline only flush practice. This practice change does not appear to be based on evidence in the literature or the results of their own research. However, they do report anecdotally that there has been no increase in the use of alteplase (CathFlo: a thrombolytic) since the practice change.

The purpose of this study is to determine the safest and most effective flushing solution(s) for maintaining patency in implanted port catheters. The researchers also hope to conclude that the complication rate in patients whose ports are flushed with saline only is no greater than those of patients whose ports are flushed with the combination of saline and heparinized saline. These complications might include partial or complete obstruction, infection of the central line, and/or the onset of heparin induced thrombocytopenia.

Research Question(s):

- 1. Does a saline only flush maintain the patency of implanted port catheters at a rate comparable to a heparinized saline solution?
- 2. Is there any difference in the type and rate of complications among implanted port catheters flushed with saline versus heparinized saline?

Null Hypothesis:

We are proposing a non-inferiority trial. Thus, the null hypothesis is: Implanted port catheters flushed with saline only will experience an occlusion rate of more than 10% over the occlusion rate experienced in implanted port catheters flushed with a heparinized saline solution.

The alternative hypothesis is: Implanted port catheters flushed with saline only will experience an occlusion rate less than 10% over the occlusion rate experienced in implanted port catheters flushed with heparinized saline solution.

Background Information/Literature Review:

Care of Implanted Port Catheters at TriHealth

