Currently at TriHealth, Inc. all implanted port catheters are flushed according to the TriHealth Nursing Policy and Procedure Intravenous Site Guidelines (See Appendix A). An implanted port catheter is flushed with normal saline after IV medication, blood, or blood draws. Heparinized saline in the amount of 5 mL (concentration 100 units/mL) is used as a final flush when no IV fluids are running and before de-accessing. This is intended to maintain patency of the catheter until the next use. The same process is used at University of Cincinnati Medical Center Barrett Infusion Center, a new site added to the study in January 2018.

TriHealth wide, there is no accurate data describing either the number of port catheters that are in use or the specifics of the complication rate. This data also is lacking UCMC wide. During the period of time between May 2, 2011 and April 30, 2012, the Out-Patient Cancer Care (OPCC) at TriHealth, utilized 134 doses of alteplase (Cath-Flo) to resolve occlusions. There is no easily accessible data describing whether these were partial (flushable but without a blood return) or complete (unable to flush) occlusions. There is no easily accessible information summarizing the type of central line that had to be de-clotted; however, the majority (>95%) of central lines

utilized by cancer patients in the OPCC are single lumen implanted port catheters. During this time period, there were two patients receiving care in the OPCC whose catheters were not flushed with a heparinized saline solution. One patient has documented HIT, and the other has a reported heparin allergy. Both patients have been able to maintain patent catheters with saline only flushes. Hospital wide, information related to the diagnosis of HIT, as it relates to type of Heparin exposure (e.g., subcutaneous or IV Heparin or the use of heparinized saline) is not available. There are no data available that demonstrates that patients with implanted port catheters who have developed a partial or complete occlusion developed bacteremia or central line infection due to the presence of fibrin on their catheter. Development of a fibrin sheath on the catheter is common after placement of an implanted port catheter (Gallieni, Pittiruti, & Biffi, 2008). The fibrin sheath may then become seeded with microorganisms which may disseminate into the blood stream. Both catheter-related thrombus and bacteremia are potentially life-threatening conditions.

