Based on the literature and our own experience we estimated an approximate occlusion rate of 20% with the standard treatment (saline + heparinized saline flush as described above). The power analysis conducted by [name] determined that, using a two-group normal approximation test of proportions with a one-sided .05 significance level, a sample size of 198 participants per group will have 80% power to reject the null hypothesis that the proposed method is not inferior (i.e. the difference in proportions between the proposed method and the standard method is greater than 0.10). Thus, we will continue data collection until 198 have been completed in each group for a total of 396 study participants who completed 6 months of data collection. To date (July 3, 2019), 69.7% of patients enrolled in the study are able to complete 6 months of data collection without withdrawing for an exclusion criterion (ex: transferring to hospice, being started on an anticoagulant, etc). Therefore, we plan to consent 575 patients to result in 396 who complete the study. Once 396 patients have completed 6 months of data collection will stop and any remaining active participants will be withdrawn from the study.

Data Collection:

Independent Variables: Method for flushing implanted port catheters:

• 20 mL of saline followed by 5 mL of Heparinized saline in a concentration of 100 units/mL

OR

• 20 mL of saline only

Dependent Variables:

Primary Outcomes

- Occurrence of first complete (can neither withdraw blood nor flush the catheter) occlusion
- Occurrence of first partial (able to flush but unable to withdraw blood) occlusion
- Frequency with which alteplase (CathFlo) has to be utilized to resolve an occlusion

Secondary Outcomes

- Number of subsequent occurrences of complete or partial occlusions after the first occurrence.
- Amount of time in days that a port remains patent (flushes easily and able to obtain a blood return).
 - Amount of time between entrance in study and first incidence of partial or complete occlusion
 - Amount of time between incidences of partial or complete occlusion.
- Occurrence of other complications:
 - Central Line-Associated Blood Stream Infection (CLABSI) a laboratory-confirmed (recognized pathogen cultured from one or more blood cultures; organism cultured from blood is not related to an infection at another site) blood stream infection that is considered central line associated (CDC, 2012).
 - Develops complication related to Heparin

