Potential risks for study participants in either arm of the study include partial occlusion (can instill flush solution but not withdraw blood) and complete occlusion (can neither instill flush solution nor withdraw blood). Study participants could require removal of the port if an occlusion cannot be resolved, and possibly require re-insertion of a new implanted port. In the event of any occlusion, alteplase (CathFlo) in the policy established dose and frequency (see Appendix A) will be instilled to resolve the occlusion. Study participants whose implanted ports are found occluded on three (3) consecutive visits to the treatment center will be excluded from further data collection, i.e., their participation in the study will be terminated. The standard flushing as prescribed by the site's policy or as prescribed by the attending physician will be used. Study participants whose occlusion cannot be resolved with alteplase and require removal of the port will also be terminated and excluded from further data collection. Patients who develop port infections necessitating port removal will be terminated and excluded from further data collection. Study participants who develop HIT (heparin induced thrombocytopenia) or other heparin allergy will be terminated and excluded from further data collection. Likewise, patients who have thrombotic or embolic phenomenon requiring therapeutic anticoagulation will be terminated and excluded from further data collection. If a participant in the intervention group receives clinical care and their port is flushed with heparin (following standard hospital policy), the participant will be withdrawn from the study.

The study will be closed if there is evidence that study participants in the intervention arm experience implanted port occlusion at a disproportionate rate. The amount of alteplase (CathFlo) used in each group will be assessed each

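### Thrombotic or embolic events and port removal end participation but are not outcomes, so the comparison of complications by arm is incomplete, with any bias in an unknown direction

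*Combined protocol and SAP*

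**What the plan says.** Purpose of Study sets the aim of finding the safest and most effective flush. Research question 2 reads: "Is there any difference in the type and rate of complications among implanted port catheters flushed with saline versus heparinized saline". The text just before it gives obstruction, central line infection and HIT as examples of complications.

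Data Collection lists the outcomes:
- Primary: first complete occlusion, first partial occlusion, and use of alteplase.
- Secondary, under other complications: CLABSI, and the item "Develops complication related to Heparin", which is broken down into HIT (a positive antibody test) and other heparin allergy.

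Experimental Aspect of the Study lists events that end participation. They include HIT or heparin allergy, port infection requiring removal, and port removal for an occlusion that alteplase does not resolve. It then adds that "patients who have thrombotic or embolic phenomenon requiring therapeutic anticoagulation will be terminated and excluded from further data collection". The sample-size text under Recruitment gives the start of an anticoagulant as an example of why participants do not complete.

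Statistical Analysis plans group comparisons on the dependent variables. The interim analyses look at first occlusions, and the monthly monitoring looks at alteplase use.

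On seriousness, Care of Implanted Port Catheters at TriHealth states: "Both catheter-related thrombus and bacteremia are potentially life-threatening conditions".

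**The concern.** The protocol names two potentially life-threatening conditions together. Bacteremia became an outcome through CLABSI. Catheter-related thrombus is counted only when it shows itself as an occlusion. A thrombosis or embolism that leads to anticoagulation while the port still flushes and draws is counted nowhere; it only removes the participant.

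HIT and heparin allergy also end participation, but both are on the outcome list. Two of the three listed other complications can arise essentially only with heparin. No listed item beyond occlusion covers clinical thrombosis in either arm.

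What is at stake is the answer to research question 2 and any statement about which flush is safest. The trial could report its complication comparison as planned and say nothing about a serious harm that the protocol itself foresees.

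**Working it through.** **1. The plan's own figure.** The inputs, all from the sample-size text under Recruitment, are: "we estimated an approximate occlusion rate of 20% with the standard treatment"; a one-sided 5% level with a normal approximation for two proportions; the statement that "a sample size of 198 participants per group will have 80% power to reject the null hypothesis"; and a margin under which "the difference in proportions between the proposed method and the standard method is greater than 0.10". Taking the saline rate as 20% too (not stated separately):

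n = (1.645 + 0.842)² × (0.20×0.80 + 0.20×0.80) / 0.10² = 6.18 × 0.32 / 0.01 ≈ 198 per group.

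This reproduces the stated 198. Also 396 / 0.697 gives 569 (rounded up), against 575 planned. The sizing concerns occlusion only and is not affected by this point.

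**2. Outcome list against termination list.**

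| Event | Ends participation | Counted as an outcome |
|---|---|---|
| HIT or other heparin allergy | Yes | Yes, secondary |
| Port infection with removal | Yes | Infection yes, where it meets the CLABSI definition; removal no |
| Unresolved occlusion with removal | Yes | Occlusion yes, primary; removal no |
| Thrombosis or embolism needing therapeutic anticoagulation | Yes | No, unless the port also occluded |

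Only the last row can be lost entirely. In the two removal rows, what is lost is mainly severity: a partial occlusion cleared by one alteplase dose counts the same as a lost port.

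**3. Where the uncounted events fall.** 575 − 396 = 179 consented participants are expected not to complete. Those terminated for thrombosis are among them. Their number cannot be derived.

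**4. Illustration of what omission could do.** The background section gives HIT incidence as 1% to 5% of patients exposed to heparin. Apply this to the control arm and assume 0% with saline. The listed heparin harms then give saline minus heparin = −1 to −5 points, or 0.01 × 198 ≈ 2 to 0.05 × 198 ≈ 10 events per 198. Let x be the unlisted difference in thrombosis (saline minus heparin). The documents give no value, so x is assumed to lie between −5 and +5 points. Adding the risks:
- x = +5, HIT 1%: 5 − 1 = +4 points
- x = +5, HIT 5%: 5 − 5 = 0
- x = 0: −1 to −5 points
- x = −5, HIT 5%: −5 − 5 = −10 points

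So counting these events could reverse the comparison, leave it alone or strengthen it, depending wholly on an unknown x. The 1% to 5% is for heparin exposure in general; the protocol gives no rate for flushes and describes no routine antibody testing.

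**5. Precision if the events are counted.** Two-sided 5% test, pooled variance under the null, assumed rates:
- 2% versus 5%, 198 per arm: Φ[(0.03 − 1.96 × 0.01847) / 0.01841] = Φ(−0.337) = 37%
- 2% versus 7%, 198 per arm: 67%
- With all 575 randomised (about 288 per arm): 50% and 83%

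For 2% versus 5% with 288 per arm, the 95% confidence interval half-width is 1.96 × √[(0.02×0.98 + 0.05×0.95)/288] = 1.96 × 0.0153 ≈ 3.0 points.

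**The case against.** The strongest reply has four parts.

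- **Occlusion is itself a complication.** The text before research question 2 says so, and occlusion is the primary outcome. This stands: the main harm expected from omitting heparin is measured. A reader might infer that a participant who loses the port adds nothing to the comparison. The documents do not support that, because the occlusion or infection that led to removal is largely counted already.
- **No tilt towards saline is shown.** A reader might infer one from a list in which two of three items are heparin harms. But the background says that HIT can lead to venous thrombosis, pulmonary emboli, stroke or myocardial infarction, so counting such events could add to the heparin arm. It also says that a fibrin sheath may be seeded with organisms, so CLABSI could count against saline. This stands as well.
- **Termination is symmetric.** HIT, allergy and infection with removal end participation too. If the analysis were confined to the 396 six-month completers, HIT cases would also drop out, and the protocol does not say clearly who is analysed. This does not rescue the plan: the listed complications need the same clarification.
- **The events may be recorded.** The Face Sheet is updated as complications occur, and its content (Appendix C) is not in the available text. True, but recording is not a planned comparison.

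The reply leaves one gap open: a thrombosis or embolism without port occlusion is in no outcome and no planned analysis.

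**Conclusion.** The point holds as one of incompleteness. For a trial that asks which flush is safest, a serious foreseen event has no planned comparison by arm, and port loss is not distinguished from milder occlusion.

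The text does not support saying that the result would be biased towards saline. The size and direction depend on thrombosis rates by arm that the documents do not give. The illustrative range of −10 to +4 points rests on an assumed thrombosis difference of −5 to +5 points, a HIT rate for general heparin exposure, and no HIT with saline. It shows only that the sign is not fixed.

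The primary non-inferiority decision on occlusion is untouched. This is a low-cost improvement that bears on research question 2 and on the safety claim.

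**What to change.** Add two items to Secondary Outcomes:
- (a) thrombotic or embolic event requiring therapeutic anticoagulation;
- (b) port removal for unresolved occlusion or for infection, reported as a severity outcome.

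State in Statistical Analysis that the terminating event is itself counted, by randomised arm, for every randomised participant including those terminated. Report HIT, other heparin allergy and CLABSI on the same basis. Present differences with confidence intervals, as descriptive results.

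The cost is a little extra coding of the termination reason, which sites must already establish in order to apply the termination rules. Whether a thrombosis was related to the port goes beyond what those rules require, so attribute it only where the chart already records it. These events are probably rare, so power will be low and the intervals wide. No visits, tests, sample size or clinical management change.

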Participants in the control group will have their implanted port catheters flushed according to the established site's policy. Following the use of the port catheter with no continuous fluids running, or before de-accessing a port catheter (removing the port needle), the port will be flushed with 20 ml of normal saline and 5 ml of heparinized saline in the concentration of 100 units of heparin per ml.

Participants in the intervention group will have their ports flushed with normal saline only. That is, following the use of the port catheter with no continuous fluids running, or before de-accessing a port catheter (removing the port needle), the port will be flushed with 20 ml of normal saline. Turbulent flushing technique (the solution is injected using a push/pause technique every 1 mL) will be used in both groups and all accessed port catheters will have a neutral displacement connector. The MicroCLAVE[®] Clear displacement connector (ICU Medical, Inc., San Clemente, CA, USA) is the current product in use. Participants in both groups will be seen in a TriHealth Cancer Institute Infusion Center or the UCMC Barrett Infusion Center at a frequency consistent with their individual treatment plan and as outlined in the site's policy. Participants will remain in the study for 6 months or until they experience one of the potential risks noted below. Participants will be considered as having completed the study if they participate for 6 months.

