month for monitoring purposes. Additionally interim data analysis will occur (1) once 1/3 of the participants have been enrolled in each group; (2) once 2/3 of the participants have been enrolled in each group (3) at the conclusion of the study. These intervals are based on the recommendation of our CCTST consultant [name]. The variable of interest in the interim data analysis at time (1) and (2) will be the occurrence of first partial occlusion plus the occurrence of the first complete occlusion in each group. At final analysis the occurrence of first partial occlusion and first complete occlusion will be considered together as well as separately in each group. [name] also advised that to control for the Type I error rate not to exceed the nominal .05 level, the p-value should be adjusted at each data interim analysis. [name] used the O'Brien Fleming alpha spending method to calculate the alpha levels for each interim analysis (O'Brien & Fleming, 1979). Thus, in order to reject the null hypothesis that the proposed procedure will produce a failure rate greater than 10% over the occlusion rate experienced using the standard procedure, the p-value at the 1st, 2nd and final analysis should be compared with an alpha value of 0.0006, 0.0151 and 0.0471 respectively. Thus if, using the p-values noted, interim calculations at time (1) or time (2) note a significant increase in the occlusion rate among participants in the intervention group, the study will be prematurely closed.

The undertaking of this research does require the participation of other personnel, facilities or departments other than those used in data collection. In the event the study participant is admitted to the hospital or requires some intervention using their implanted port catheter (e.g., CT scan with contrast), the study participant will have an information card describing his/her participation in the study and the group to which he/she has been randomized, so that the assigned flush solution is used, and integrity of the study can be maintained. The study participant will receive the card with instructions at the time of his/her enrollment in the study (see Appendix E Wallet Study Card).

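### Only saline-arm participants are withdrawn from the study after an outside heparin flush, so attrition differs by arm by rule and can bias the comparison, probably but not certainly towards non-inferiority

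*Combined protocol and SAP*

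**What the plan says.** All references are to the combined protocol and SAP.

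- **The rule.** The paragraph on potential risks in Experimental Aspect of the Study reads "If a participant in the intervention group receives clinical care and their port is flushed with heparin (following standard hospital policy"), and the consequence is that "the participant will be withdrawn from the study". This ends participation, not only the assigned flush.
- **The control arm.** The same section defines the control procedure: "the port will be flushed with 20 ml of normal saline and 5 ml of heparinized saline". A hospital heparin flush is therefore on-protocol for a control. No matching rule covers a control who receives a saline-only flush elsewhere.
- **Other withdrawal triggers.** Occlusion on three consecutive visits, port removal, port infection, HIT or heparin allergy, and therapeutic anticoagulation are all written without reference to arm.
- **Where the exposure arises.** The same section anticipates it: "In the event the study participant is admitted to the hospital or requires some intervention using their implanted port catheter". Its example is a contrast CT scan. Participants carry a wallet card showing their group, "so that the assigned flush solution is used, and integrity of the study can be maintained".
- **Who is counted.** The power analysis under Recruitment sets a target of 198 per group who complete 6 months, and reports that "69.7% of patients enrolled in the study are able to complete 6 months of data collection". That figure is not split by arm or by reason.
- **Analysis.** Statistical Analysis names t-test, Chi-Square or Fisher's exact test. It defines no intention-to-treat or per-protocol population and does not say how withdrawn participants, or their occlusions before withdrawal, are handled.

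**The concern.** The same event in hospital care ends participation in one arm and changes nothing in the other. After randomisation, the saline arm loses the participants who were treated elsewhere and given heparin, while their counterparts in the control arm stay. With a target defined by completers and no stated population, the analysed groups need no longer be comparable.

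In a non-inferiority trial, anything that lowers the observed saline rate below its true value makes a false claim of non-inferiority more likely. The loss also cannot be repaired at analysis: once a participant is withdrawn, the remaining Record of Flushes is not collected, so an all-randomised analysis would have outcomes missing by rule in one arm.

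**Working it through.** **1. The plan's own figure.** Inputs from the power analysis: 20% in both arms, margin 0.10, 80% power, "using a two-group normal approximation test of proportions with a one-sided .05 significance level".

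n = (1.645 + 0.842)² × (0.20×0.80 + 0.20×0.80) / 0.10² = 197.8, so 198 per group. This matches the plan. Enrolment: 396 / 0.697 = 568.1, so 569, against 575 planned; this is close enough.

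**2. Set-up for the bias check.** Put the truth on the margin: control 0.20, saline 0.30, 198 analysed per arm. A sound procedure then declares non-inferiority 5% of the time. I use a single test at 0.05. The interim plan says that p-values "should be compared with an alpha value of 0.0006, 0.0151 and 0.0471 respectively"; at 0.0471 the starting point would be 4.7%, and the pattern is the same.

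Two inputs are assumptions, because the documents give neither:
- h = share of the saline arm withdrawn under this rule
- r = their occlusion risk relative to the rest of that arm

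With the whole-arm saline rate fixed at 0.30, the risk among those not withdrawn is p = 0.30 / (1 − h + h·r).

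False non-inferiority rate = Φ[(0.10 − d)/SE − 1.645], where d is the expected observed difference and SE = √[(0.20×0.80 + pₛ(1 − pₛ))/198], with pₛ the observed saline rate.

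**3. Withdrawn participants excluded (completers only).** Here pₛ = p.

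| h | r | pₛ | d | False non-inferiority |
|---|---|---|---|---|
| any | 1 | 0.300 | 0.100 | 5.0% |
| 2% | 1.5 | 0.297 | 0.097 | 5.8% |
| 5% | 1.5 | 0.293 | 0.093 | 7.0% |
| 10% | 1.5 | 0.286 | 0.086 | 9.5% |
| 10% | 2 | 0.273 | 0.073 | 15.8% |
| 10% | 0.5 | 0.316 | 0.116 | 2.2% |

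Worked row, h = 10%, r = 2: pₛ = 0.30/1.10 = 0.2727; SE = √[(0.1600 + 0.1983)/198] = 0.0425; (0.10 − 0.0727)/0.0425 − 1.645 = −1.00; Φ = 0.158.

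**4. Withdrawn participants kept in the denominator, second half of follow-up lost.** Observed risk among them = 1 − √(1 − r·p).

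At h = 10%, r = 1: 1 − √0.70 = 0.163; pₛ = 0.9×0.300 + 0.1×0.163 = 0.286; false non-inferiority 9.2%. At r = 0.5 it is 7.1%, and at r = 2 it is 12.9%. The tilt is towards non-inferiority at each of these risk ratios, because events are missed in one arm only.

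**5. Earlier occlusions counted, only event-free withdrawals dropped.** Same truncation, h = 10%.
- r = 1: pₛ = 0.286/(0.9 + 0.1×0.163) = 0.312; false non-inferiority 2.7%.
- r = 2: pₛ = 0.278/(0.9 + 0.1×0.326) = 0.298; false non-inferiority 5.5%.

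**6. Everyone retained in the assigned arm.** If 10% of the saline arm spend half of follow-up under heparin, and their risk is then midway between the saline and control values:
- r = 1: pₛ = 0.9×0.30 + 0.1×0.25 = 0.295; difference 0.095; false non-inferiority 6.3%.
- r = 2: their risk is (0.545 + 0.364)/2 = 0.455; pₛ = 0.9×0.273 + 0.1×0.455 = 0.291; difference 0.091; false non-inferiority 7.6%.

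**The case against.** A reader might infer that the rule strips the sicker, hospital-treated patients out of the saline arm and so tilts the trial towards its hoped-for result. The documents do not support that as a finding. They nowhere say that these participants are sicker or occlude more often. The trigger is clinical care plus a heparin flush, and the protocol's own example, a contrast CT scan, need not mark frailty. Several triggers that plausibly take out high-risk participants apply in both arms. Under exclusion, equal risk gives no bias and lower risk tilts against saline. Under the handling in step 5, the result is conservative at equal risk.

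The number affected is also unknown. The 30.3% who do not complete cover both arms and all reasons, and the protocol's examples of those reasons are hospice transfer and starting an anticoagulant. The wallet card acts directly on h, and at h = 2%, r = 1.5 the rate is only 5.8%.

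Finally, a per-protocol analysis is not a clean check. Even with one deviation definition for both arms, it would remove mainly saline participants, because a heparin flush is no deviation for a control.

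All of this stands as a limit on direction, size and remedy. It does not remove the defect: the rule is written for one arm, it ends data collection, and nothing in the analysis section recovers what is lost. The card cannot be assumed to reduce h to zero, since the protocol keeps a rule for when heparin is given anyway.

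**Conclusion.** The concern holds in limited form. Attrition differs by arm by rule, after randomisation, in a trial that counts completers and names no analysis population. This can bias the comparison, probably but not certainly towards non-inferiority.

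Over the scenarios shown, the false non-inferiority rate at the margin runs from 2.2% to 15.8% if withdrawn participants are excluded, and from 7.1% to 12.9% at h = 10% if they are kept with half their follow-up lost. These ranges rest on assumed h and r, on true rates of 20% and 30%, on 198 analysed per arm and, for truncation, on losing half of follow-up. The conclusion thus depends on a handling choice that the plan does not state. Confidence is moderate: the one-arm rule is certain from the text, while the direction and size of its effect are not.

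**What to change.** 1. Replace withdrawal from the study with recording the off-assignment flush as a protocol deviation, defined the same way in both arms (heparin given to a saline participant, saline only given to a control). This concerns data collection only; which flush the participant then receives is a clinical matter outside this point.
2. Continue the Record of Flushes to 6 months for these participants.
3. Make the primary analysis all-randomised, with occlusions counted in the assigned arm.
4. Report deviations and withdrawals by arm and reason, including those already withdrawn under the current rule, so that h can be seen.
5. Add a per-protocol sensitivity analysis using the common deviation definition, and state its limits: it will still remove mainly saline participants, and the all-randomised analysis keeps some heparin exposure that dilutes a true difference. Both can err towards non-inferiority, so their agreement is supportive and is not a safeguard.

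The cost is a short amendment, continued routine data collection and some dilution: the boundary difference of 0.100 becomes about 0.091 to 0.095 if 10% of the saline arm are exposed for half of follow-up. If r were exactly 1, retention would carry slightly more error than exclusion (6.3% against 5.0%); at r = 2 it carries about half as much (7.6% against 15.8%). Retention also yields the outcome data that the current rule discards.
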